5.6 Data Analysis

- Provide sample size determination and analysis (include anticipated rate of screen failures, study discontinuations, lost to follow-up etc.).**

Our primary measure to assess dynamic balance during walking is the Lane Width Optimization Test. The test challenges participants to maintain their medio-lateral COM position within a target lane during treadmill walking. If successful, the difficulty of the task becomes progressively more difficult by continually narrowing the width of the target lane until the participant is unable to maintain the target position. The lateral COM excursion per stride during the narrowest lane width achieved **provides a quantitative measure of dynamic balance during gait**. A reduction in the minimum lateral COM excursion following training would indicate improved dynamic balance during gait.

We performed a power analysis to determine the minimum sample size required to detect significant changes in dynamic balance using the lane width optimization test. To estimate the population variability, we used data from 13 individuals with iSCI, having similar characteristics to the target population, performing unassisted treadmill walking [102]. We found that typical lateral COM excursion per stride during preferred speed treadmill walking was 0.083 ± 0.014 m (mean \pm standard deviation). To estimate effect size, we used pre- and post-intervention data from three individuals with iSCI who received 16-18 high intensity locomotor training sessions performed in the movement amplification environment. Following the intervention, these individuals improved dynamic balance (decreased their lateral COM motion excursion during walking) by 32-36%. To detect a 20% difference in improvements in dynamic balance between training groups we will need a sample size of 7 individuals per group at $\alpha = 0.05$ and a power of 80%. We plan to enroll 46 individuals. A recent locomotor training intervention using individuals with iSCI, conducted by one of our study team members at a nearby facility, lost 12% of their participants to drop out [60]. With a conservative estimate that we will lose 20% of participants to drop out, an initial enrollment of 46 individuals would yield 14 high functioning and 14 low functioning participants (stratified based on the gait speed). This number, double that estimated by the power analysis, should be sufficient to assess training effects on dynamic balance.

We plan to enroll 46 participants with iSCI in the trial. Veterans will be recruited from the Spinal Cord Injury Service at Edward Hines Jr. VA Hospital. During the last three years, the Hines Spinal

Cord Injury Service saw 553 unique patients with SCI. Our research team includes a highly experienced clinical coordinator located at the Edward Hines Jr. VA Hospital. [name] will work with clinicians in the Spinal Cord Injury Service to identify, contact, and screen potential study participants. As needed, additional Veteran and non-Veteran participants will be recruited through the Shirley Ryan AbilityLab. The Shirley Ryan AbilityLab maintains the *Clinical Neuroscience Research Registry* a database of interested, potential study volunteers with SCI. Of these volunteers greater than 215 individuals identify that they are able to walk in therapy, home or the community. [name], a co-Investigator on this proposal, jointly oversees the volunteer database and will ensure access. Collectively, the potential pool of participants available between the Edward Hines Jr. VA Hospital and the Shirley Ryan AbilityLab will be more than adequate to meet the requirements for the proposed trial.

- **Describe how, where and by whom the data will be analyzed.**

The PI, research physical therapist, research engineers, and biostatistician will work collaboratively to analyze the data. The data will be analyzed at Northwestern University.

Specific Aim 1: To test if our primary measure, changes in dynamic balance during walking, is different between the two groups following the two interventions, we will compare changes in participants' COM lateral excursion during the lane width optimization test across the four assessment periods (BSL, Mid, Post, Follow Up) and between intervention groups (Control and Experimental). To account for the correlation that arises from measuring multiple data points within each participant over time (i.e. data measured from the mid- assessment period from a specific participant will bear more resemblance to data measured from the BSL- assessment period from the same participant than a different participant) we propose to model the primary outcome using a linear mixed effects model. We will use an indicator variable for the group assignment, i.e. 1=Experimental, 0=Control, to test for the effect of intervention while controlling for potential confounders such as initial walking speed, severity and location of the SCI, spasticity, and age. The strength of the linear mixed effects models is that it can accommodate multiple data points from a single participant and can also handle missing data when data is missing at random. We will apply a similar strategy for fitting a secondary analysis to examine changes in preferred walking characteristics (average and variability of step width, step length, and minimum lateral MOS) and outcome measures (10 MWT, FGA, ABC etc.) across the four assessment periods and between intervention groups. We will transform the variables, such as log-transformation, as needed to meet the model assumption of normality.

Specific Aim 2: To test if our primary measure, changes in steps per day, are different following the two interventions, we will compare changes in participants' average steps per day across the three assessment periods (BSL, Post, Follow Up) and between intervention groups (Control and Experimental). Similar to the methods proposed above, we will model the primary outcome using a linear mixed effects model. We will use an indicator variable for the group assignment, i.e. 1=intervention, 0=control, to test for the effect of intervention while again controlling for potential confounders such as initial walking speed, severity and location of spinal cord injury, spasticity, and age.

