Improving dynamic balance after iSCI is very challenging because sensory-motor impairment limits the nervous system's capacity to detect movement errors. Error detection is necessary for updating the nervous system's internal model to correctly relate motor commands to their resulting movement. On a step-by-step basis, an internal model that poorly predicts motion limits the nervous system's ability to anticipate predictable balance challenges during gait (i.e. periodic COM motion). As such, individuals with iSCI often select passively strategies (e.g. wide steps) that maintain dynamic balance with minimum requirements from the nervous system to anticipate ongoing balance demands. These passive strategies are inflexible, inefficient [13], and limit walking speed [14]. Experimental interventions that amplify self-generated movements (e.g. error augmentation) may accelerate motor learning by augmenting sensory-motor feedback [15] and thus allowing the impaired nervous system to identify otherwise imperceptible errors. Such interventions could enhance dynamic balance by recalibrating the internal model to better predict COM motion. We have developed a cable-driven robot that creates a movement amplification environment by applying a continuous viscous force field to the pelvis that is proportional in magnitude to a participant's real-time COM velocity [16]. Our purpose is to investigate if locomotor training performed in a movement amplification environment can effectively improve dynamic balance and increase participation in walking activities of individuals with iSCI.

Specific Aim 1: To evaluate if locomotor training performed in a movement amplification environment is effective for improving dynamic balance of individuals with iSCI.

Hypothesis 1: Improvements in dynamic balance during walking will be greater when locomotor training is performed in a movement amplification environment when compared to a traditional treadmill environment.

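### The 7 per group cannot be reproduced from the inputs printed in section 5.6 (a two-sided raw-scale t test needs 13), and 46 enrolled less 20% is about 36 completers, not 28

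*Combined protocol and SAP*

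**What the plan says.** The sample size paragraph is in section 5.6. The variability comes from 13 people with iSCI walking normally on a treadmill: "typical lateral COM excursion per stride during preferred speed treadmill walking was 0.083 ± 0.014 m". The pilot effect is a 32–36% reduction in three people trained in the movement amplification environment, with no control group. The requirement follows: "To detect a 20% difference in improvements in dynamic balance between training groups we will need a sample size of 7 individuals per group". Alpha is set to 0.05 and power to 80%.

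The paragraph then turns to enrolment. Its allowance for loss reads: "With a conservative estimate that we will lose 20% of participants to drop out". From this it derives the expected completers: "an initial enrollment of 46 individuals would yield 14 high functioning and 14 low functioning participants". It concludes: "This number, double that estimated by the power analysis, should be sufficient to assess training effects on dynamic balance".

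Three other places bear on this:

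- Hypothesis 1 in section 3.0 is directional: "Improvements in dynamic balance during walking will be greater when locomotor training is performed in a movement amplification environment" than in a traditional treadmill environment.
- The Aim 1 analysis in section 5.6 is a linear mixed model over four visits, with the option "We will transform the variables, such as log-transformation, as needed to meet the model assumption of normality".
- Section 6.0 supports its safety-monitoring arrangement partly by saying that the study has fewer than 40 participants. Sections 5.1, 5.2 and 5.6 all say 46.

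**The concern.** Two figures carry the justification: the requirement of 7 per group and the expected number of completers. The first cannot be checked, because the paragraph names no test, scale, sidedness, visits or within-person correlation, and the simplest between-group calculation gives nearly twice as many. The second contradicts the dropout rate in its own sentence. The claimed twofold margin is the ratio of the two, so it inherits both problems.

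There is also a mismatch of measure. The SD of 0.014 m is a cross-sectional SD from ordinary preferred-speed walking. The primary measure is COM excursion at the narrowest lane reached in the Lane Width Optimization Test, and the stated target is a difference in improvement.

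What is at stake is whether a reader can rely on the stated power and margin. The trial could still be large enough even though the printed argument does not show it.

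**Working it through.** **Inputs (section 5.6 unless noted)**

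| Input | Value | Status |
|---|---|---|
| Mean excursion | 0.083 m | printed |
| SD | 0.014 m | printed; preferred-speed walking |
| Between-group difference | 20%, taken as 0.20 × 0.083 = 0.0166 m | 20% printed; its base is assumed |
| Alpha, power | 0.05, 80% | printed; sidedness not stated |
| Allocation | 1:1 | assumed |
| Enrolled, dropout | 46, 20% | printed |
| Pre-post correlation | none | not printed; range shown below |

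**Step 1. Trying to reproduce 7 per group.** On the raw scale, d = 0.0166 / 0.014 = 1.186. This takes 0.014 m as the SD of the quantity analysed; for change scores that means a correlation of 0.5, since the SD of change is SD × √(2(1 − r)).

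The normal formula is n = 2(z_alpha + z_power)² / d². Two-sided, this is 2(1.960 + 0.842)² / 1.186² = 11.17, so 12. One-sided it is 8.80, so 9. The t-test figures use the noncentral t distribution.

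On the log scale, the SD is √ln(1 + (0.014/0.083)²) = 0.1675. The difference is −ln 0.8 = 0.223, so d = 1.332.

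| Two-sample comparison | n per group, t test | n per group, normal formula | t-test power at 7 |
|---|---|---|---|
| Raw, two-sided | 12.20 → 13 | 11.17 → 12 | 53% |
| Raw, one-sided | 9.55 → 10 | 8.80 → 9 | 67% |
| Log, two-sided | 9.90 → 10 | 8.84 → 9 | 63% |
| Log, one-sided | 7.74 → 8 | 6.97 → 7 | 76% |

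Only the one-sided normal approximation on the log scale returns 7, and the exact t power there is 76%.

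**Step 2. Other routes to 7.** For 80% power at 7 per group, a two-sided t test needs d = 1.632. Starting from 1.186, that takes a pre-post correlation of about 0.74 for change scores or 0.69 with baseline adjustment, where the residual SD is SD × √(1 − r²). The two-sided requirement per group moves with the correlation as follows.

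| Correlation | 0.3 | 0.5 | 0.7 | 0.8 |
|---|---|---|---|---|
| Change scores | 17 | 13 | 8 | 6 |
| Baseline-adjusted | 12 | 10 | 7 | 6 |

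Averaging three post-baseline visits with baseline adjustment gives about 86% and 88% power at 7 per group for correlations of 0.3 and 0.5. That assumes equal correlations between visits and a constant effect. A one-sided one-sample test on the raw scale gives 6.0005, which rounds up to 7, but it is not the between-group comparison claimed.

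**Step 3. Completers.** No modelling assumption is needed.

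- Overall: 46 × 0.80 = 36.8. Printed: 14 + 14 = 28.
- Per gait-speed stratum: 23 × 0.80 = 18.4. Printed: 14.
- Loss implied by 28 from 46: 1 − 28/46 = 39%.
- Enrolment that would leave 28 after 20% loss: 28 / 0.80 = 35.

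The two 14s are gait-speed strata, as section 5.1 defines them, not treatment arms.

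**Step 4. The margin.** Completers are divided by twice the per-group requirement.

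| Basis | Required total | 28 completers | 36 completers |
|---|---|---|---|
| Raw t, two-sided | 26 | 1.08 | 1.38 |
| Raw t, one-sided | 20 | 1.40 | 1.80 |
| Log t, two-sided | 20 | 1.40 | 1.80 |
| Log t, one-sided | 16 | 1.75 | 2.25 |
| Baseline-adjusted, two-sided, r = 0.7 | 14 | 2.00 | 2.57 |

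**Step 5. Is 46 enough?** Raw-scale two-sided power is 0.855 at 14 per arm and 0.933 at 18. Thirteen per group needs 26 / 0.80 = 32.5, so 33 enrolled. Seventeen per group (change scores, r = 0.3) needs 34 / 0.80 = 42.5, so 43. Both are within 46.

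**The case against.** The best defence is that baseline adjustment is itself a standard two-sided between-group method and gives 7 at a correlation of 0.7, with power of about 81%. The planned analysis is a mixed model over four visits, which draws on exactly that correlation, so 7 may come from a reasonable calculation that was not written down. This stands to the extent that 7 is unexplained rather than impossible. It does not supply the missing inputs: across correlations of 0.3 to 0.8 the change-score requirement runs from 17 to 6 per group, and section 5.6 ties 7 to no point in that range.

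The figure of 13 is also conditional, and that stands. It takes 20% to mean 20% of the 0.083 m mean, which is the natural reading but not the only one. If it meant 20% of a pilot improvement of about 34%, then d = 0.34 × 1.186 = 0.40 and the same t test would need 98 per group. Nothing suggests this was intended, but the base of the percentage should be stated.

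Part of the pilot description in section 2.0 was not in the text examined, so the statement that the assumptions are missing covers the visible text. The power paragraph itself appears complete.

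Finally, the completer slip understates the expected sample and so errs on the cautious side. That is true and limits the harm, but no reading makes 46 less 20% equal 28.

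**Conclusion.** The point holds. The completer count is an arithmetic error: about 36, not 28. The enrolment of 46 also conflicts with the description in section 6.0 of fewer than 40.

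The 7 per group is unsupported as printed. A two-sided two-sample t test needs 13 and has 53% power at 7. This rests on 20% of the mean, 0.014 m as the SD of the analysed quantity, and equal allocation. The twofold margin is therefore conditional: it fails in every two-sided t-test case without baseline adjustment shown above, and holds with baseline adjustment at a correlation of about 0.7.

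The trial is not shown to be underpowered. The defect lies in the printed justification and should be fixed.

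**What to change.** In section 5.6:

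1. Either print the test, scale, sidedness, visits and correlation that give 7, with a source for each, or restate the requirement as 13 per group under a two-sided raw-scale two-sample t test with SD 0.014 m. The first option sits closer to the planned mixed model.
2. State what the 20% is a percentage of.
3. In either case, show the requirement over a range of correlations, as in the change-score and baseline-adjusted table above.
4. Correct the completers to about 36 (18 per arm under equal allocation, about 18 per gait-speed stratum), quote power at that number, and recompute or remove the claim of a twofold margin.
5. If COM excursion data from the 12 people who performed the Lane Width Optimization Test (section 2.0, Preliminary Studies) are available, use their SD in place of 0.014 m. Section 2.0 reports only lane-width correlations for them.

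In section 6.0, reconcile the participant number with 46.

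The cost is one reworded paragraph and one reworded phrase. Enrolment need not change on the assumptions above; the stated margin may become less favourable.

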Participants will be stratified by gait speed (half of the participants will have a preferred over ground gait speed ≥ 0.5 m/s and half of participants will have a preferred over ground gait speed < 0.5 m/s) and then randomized into two locomotor intervention groups:

The **Control group** will receive high intensity locomotor training performed on a treadmill [60].

The **Experimental group** will receive high intensity locomotor training performed on a treadmill in a movement amplification environment created by the Agility Trainer.

We will conduct **clinical outcome measures** to assess changes in functional gait and balance and quality of life. We will conduct quantitative **laboratory assessments** to evaluate changes in dynamic balance and associated gait patterns. Finally, to assess if the effects of locomotor training impact participation in walking activities outside of the laboratory/clinical setting, we will measure daily **steps taken in the home and community**.

To ensure that gait and balance are stable prior to beginning the intervention, we

will measure 10 m walk speed and Berg Balance Scale score during an initial **Screen**. These two measures will be repeated a week later during the Baseline (**BSL**) assessment session to ensure the participant's initial performance is stable. If measures are not stable, measures will be repeated a week later. If measures do not stabilize after three-weeks of testing, the participant will not be enrolled in the training intervention. Clinical outcome measures and laboratory assessments will be performed at four time points (**BSL**, **Mid**, **Post**, and **Follow Up**) encompassing the 20-session training intervention (Figure 7). Average number of steps taken in the home and community environment will be estimated from data recorded during 1-week periods occurring at three time points corresponding with **BSL**, **Post**, and at the 3-month **Follow Up**. (Figure 7).

Figure 7. Timeline of the 22 to 26 week schedule for assessments and locomotor training intervention. The length of each individual study segment is indicated.

Daily Steps Assessment	Training Intervention	Training Intervention	Daily Steps Assessment	Daily Steps Assessment
Screen 1-Day	Stepping 1-week	BSL 1-Day	Sessions 1-10 3-5 Weeks	Mid 1-Day
Screen, Consent, 10 MWT, BBS	Clinical And Laboratory Assessments		Clinical And Laboratory Assessments	Clinical And Laboratory Assessments

Locomotor Training Interventions

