6.0 Reporting

- **Include procedures for reporting unanticipated problems, serious adverse events, and protocol deviations.**

Any unanticipated deaths will be reported to both the Hines IRB and the Northwestern University IRB within 24 hours of becoming aware of them. Any serious adverse events will be reported to the Hines IRB and Northwestern IRB within 48 hours of becoming aware of the event. All unanticipated adverse events or unanticipated problems involving risks to research participants or study personal will be reported to the Hines IRB and Northwestern University IRB within 48 hours. Any adverse event directly or indirectly related to the study, such as loss of confidentiality or emotional trauma, will also be reported to the Hines IRB and the Northwestern University IRB. Privacy and Data security breaches will be reported to the Hines ISO and Northwestern University ISO immediately.

- **Include information about whether the study has a Data Monitoring Committee and if so, how often it will meet.**

[name] and [name] will jointly be responsible for carrying out the Data Safety Monitoring Plan. The decision to have [name] monitor safety of the trial was based on the simplicity and limited size of the proposed project. Specifically, the following factors were considered - the proposed study is low risk, [name] are not blinded to the study interventions, the study involves less than 40 total participants, and experimental testing and training sessions will be conducted at a single location.

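### 46 enrolled with 20% dropout leaves about 37 participants, not 14 + 14 = 28, and the monitoring rationale's figure of under 40 contradicts the planned 46

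*Combined protocol and SAP*

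**What the plan says.** Section 5.6 (Data Analysis) requires 7 participants per group and plans to enrol 46. It cites an earlier locomotor training study that "lost 12% of their participants to drop out" and then adopts a higher rate for this trial: "With a conservative estimate that we will lose 20% of participants to drop out". The same sentence concludes that "an initial enrollment of 46 individuals would yield 14 high functioning and 14 low functioning participants". The adequacy claim follows directly: "This number, double that estimated by the power analysis, should be sufficient to assess training effects on dynamic balance".

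Section 5.1 (Study Design, Protocol Overview) sets the split between strata: "Participants will be stratified by gait speed (half of the participants will have a preferred over ground gait speed" of at least 0.5 m/s, and the other half a slower one. It also describes a possible loss before training: "If measures do not stabilize after three-weeks of testing, the participant will not be enrolled in the training intervention".

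The figure of 46 appears in the study population text of section 5.1, in two places in section 5.2 (Recruitment Methods), and again in the recruitment paragraph of section 5.6.

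Section 6.0 (Reporting) says the decision on who monitors safety was "based on the simplicity and limited size of the proposed project". It lists four factors, one of which is that "the study involves less than 40 total participants".

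**The concern.** The inputs and the result of the yield calculation stand in one sentence, and the result does not follow from them. The difference is about 9 participants, too large for rounding. The doubling claim, which is the plan's only statement that the sample is large enough, refers to that result. A reader cannot tell whether the team expects to lose about 9 of 46 participants or 18. The difference bears on the analysis because section 5.7 gives no follow-up testing to anyone who withdraws, so retention decides how many people contribute Post and Follow Up data.

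The statement in section 6.0 is a separate inconsistency. Trial size is offered as a reason for the monitoring arrangement, and the size given there is not the size planned everywhere else.

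**Working it through.** **Inputs.** Enrolment N = 46 (sections 5.1, 5.2, 5.6). Dropout d = 20% assumed, 12% in the cited study (section 5.6). Half of the participants in each gait-speed stratum, so 23 each (section 5.1). Requirement 7 per group, so 2 × 7 = 14 in total (section 5.6).

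**The plan's own figures.** 14 + 14 = 28, and 28 / 14 = 2.0. The doubling claim therefore agrees with a yield of 28. What fails is the step from 46 to 28.

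**Yield from the stated inputs**, N × (1 − d):

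- Total: 46 × 0.80 = 36.8, so 36 to 37 participants.
- Per stratum: 23 × 0.80 = 18.4, against 14 stated.
- Shortfall of the stated figure: 28 / 36.8 − 1 = −0.239, or 24% too low.

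**Other routes from 46 to 28:**

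| Route | Result |
|---|---|
| 12% dropout: 46 × 0.88 | 40.5 |
| Dividing by 1.20: 46 / 1.20 | 38.3 |
| 20% and 12% compounded: 46 × 0.80 × 0.88 | 32.4 |
| 20% applied twice: 46 × 0.80 × 0.80 | 29.4 |

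Only the last comes close, and nothing in the plan supports applying 20% twice.

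**Implied loss.** 46 − 28 = 18, and 18 / 46 = 39.1%, against 46 × 0.20 = 9.2 participants at the stated rate.

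**The doubling claim with the corrected yield.** It can be read in two ways:

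- Whole sample against the total requirement of 14: 36.8 / 14 = 2.6 times.
- The requirement of 14 met once within each stratum: 18.4 / 14 = 1.3 times.

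On neither reading do the stated inputs give the figure used.

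**Section 6.0.** A total below 40 is at most 39, and 46 − 39 = 7, so the planned enrolment exceeds the stated ceiling by at least 7. The expected number of completers (36.8) is below 40, but the sentence counts total participants, and safety monitoring covers everyone who enters, including those who later drop out.

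**Back-calculation.** At 20% dropout, 28 completers correspond to 35 enrolled (35 × 0.80 = 28.0) or, with an even split by stratum and arm, 36 (36 × 0.80 = 28.8). Both are below 40. A single enrolment of 35 or 36 would thus explain both discrepancies, but the documents do not say that such a figure was ever used.

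**The case against.** The strongest objection is that the documents do not settle which number is wrong. Section 5.5 puts consent before eligibility screening, and section 5.1 keeps people with unstable measures out of training. If 46 counted people consented and about 35 started training, then 28 completers and a total below 40 would both fit. In that case, writing 18 + 18 would overstate the analysable sample, and the error could not be called conservative. This has some force: the direction of the error depends on 46 and 20% being the intended inputs. But section 5.6 attributes the yield to dropout alone and gives no screen-failure rate, although its own prompt asks for one. Going from 36.8 to 28 needs a further loss of 1 − 28 / 36.8 = 24% that is stated nowhere. The remedy should leave room for this reading.

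A second objection is that the matter is editorial: no analysis uses the figure, the case for adequacy is stronger at 36 to 37 than at 28, and the other three monitoring factors do not depend on trial size. The limited consequence is granted. Both figures nevertheless serve as stated justification, one for sample size and one for safety oversight, and both conflict with the plan.

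A third objection is that a larger multiple should not be advertised, because 7 per group is itself doubtful. With a difference of 0.20 × 0.083 = 0.0166 m and an SD of 0.014 m, a two-sided two-group comparison at 80% power needs 12 per group by normal approximation or 13 by t-test. Against 2 × 13 = 26, a yield of 36.8 is only 1.4 times. That is a fair caution about the rewording, but a separate matter from whether 46 and 20% give 28.

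**Conclusion.** Both inconsistencies hold. With 46 enrolled, 20% dropout and equal strata, the yield is 36.8 participants (18.4 per stratum), not 28 (14 per stratum). The stated figure implies 39% loss, nearly twice the rate the plan assumes. Taking 46 and 20% as the intended inputs, the error understates retention and does not weaken power; an undocumented loss before training would change that reading, not remove the inconsistency. The total given in section 6.0 is contradicted by the 46 planned throughout, which makes one of four stated reasons for the monitoring arrangement false. Nothing in the documents ties a requirement to 40 participants, so this does not show the arrangement to be inadequate. The corrections should be made; the design does not need to change. Confidence is high, since every input is stated in the plan and the arithmetic is elementary.

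**What to change.** In section 5.6, keep 46 and 20%, give the yield as about 18 + 18 (36 to 37 in total), and reword the doubling claim to match, saying whether it refers to the whole sample or to each speed stratum. If a further loss before training was assumed, state that rate instead and derive the yield from it. In that case, also say whether 46 counts people consented, randomised or starting training.

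In section 6.0, replace the figure below 40 with 46 and add one sentence confirming that the monitoring rationale still holds at that size.

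The cost is text corrections in two sections and the one confirming sentence. Enrolment and the planned analyses are unchanged.

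### Walking speed and Berg score are tested twice before training but the listed analysis starts at BSL; using both tests is a cheap, optional precision gain for two secondary outcomes

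*Combined protocol and SAP*

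**What the plan says.** Section 5.1 (Protocol Overview) states that the team "will measure 10 m walk speed and Berg Balance Scale score during an initial" visit. It continues: "These two measures will be repeated a week later during the Baseline" "assessment session to ensure the participant's initial performance is stable". A further test is possible: "If measures are not stable, measures will be repeated a week later". There is also a limit: "If measures do not stabilize after three-weeks of testing, the participant will not be enrolled in the training intervention". No numerical definition of stable is given, and confirming stability is the only use stated for the repeat.

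Section 5.6 (Specific Aim 1) compares the primary measure "across the four assessment periods (BSL, Mid, Post, Follow Up") and says "we propose to model the primary outcome using a linear mixed effects model". A similar strategy is then applied to the secondary "outcome measures (10 MWT, FGA, ABC etc.) across the four assessment periods and between intervention groups". The 10 m walk is named there. The Berg scale comes in only through the etc., although Sections 5.1 and 5.5 list it among the clinical measures taken at the same four time points. Initial walking speed is an adjustment variable in both primary models, and the visit that supplies it is not stated.

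**The concern.** Each change in walking speed or Berg score carries the measurement error of its baseline. If the baseline is the BSL test alone, that error enters in full, although a second pre-training test of the same quantity is already in hand.

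The trial is small: 46 are enrolled, and a 20% loss would leave about 37 (46 × 0.8 = 36.8). Free precision is worth having at that size. What is at stake is the width of the confidence intervals for two secondary outcomes. There is no bias at issue and no effect on either primary result.

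A smaller point is that some participants will have two pre-training values and others three. The plan does not say which of them is the initial walking speed, and that choice is better fixed before the data are seen.

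**Working it through.** The documents give no SD, reliability, correlation or power for the 10 m walk or the Berg scale, so there is no plan figure to reproduce. The calculation is algebra with stated assumptions. The ratio for one participant's change is also the ratio for the arm difference, because both arms are treated alike.

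**1. Ceiling, with no stability gate.** Take equal variance s² at each visit and a common correlation r.

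- BSL alone: Var(Post − BSL) = 2s²(1 − r).
- Mean of two: Var(Post − mean) = s²[1 + (1 + r)/2 − 2r] = 1.5s²(1 − r).
- Ratio 1.5/2 = 0.75 for any r: a 25% reduction in variance, or a 13.4% smaller standard error (1 − √0.75).

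A generalised least squares calculation for a mixed model with one or two pre-training and three later occasions also gives 25% when the arms may differ at baseline.

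**2. Baseline-adjusted form.** With adjustment for baseline, or a common baseline mean, the ratio is (1 + 2r)/(1 + r)². At r = 0.5 it is 2.0/2.25 = 0.889 (11% reduction), at r = 0.8 it is 2.6/3.24 = 0.802 (20%), and at r = 0.9 it is 2.8/3.61 = 0.776 (22%).

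**3. Effect of the stability gate.** Set the error variance of one test to 1, so that the Screen-BSL difference d has variance 2. Suppose a participant is enrolled only if |d| is within c SDs of d. The mean of the two tests is independent of d, so its error variance stays at 0.5. The error variance of BSL among those enrolled is 0.5 + Var(d | gate)/4 = 0.5 + k/2, where k = 1 − 2cφ(c)/(2Φ(c) − 1). If true responses vary between people by v error variances:

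- change from BSL: 1.5 + k/2 + v
- change from the mean: 1.5 + v
- reduction = (k/2)/(1.5 + k/2 + v)

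| Assumed gate | Pass one comparison | k | Reduction, v = 0 | v = 1 | v = 2 |
|---|---|---|---|---|---|
| none | 100% | 1 | 25% | 16.7% | 12.5% |
| 2 SD | 95% | 0.774 | 20.5% | 13.4% | 10.0% |
| 1 SD | 68% | 0.291 | 8.8% | 5.5% | 4.0% |
| 0.5 SD | 38% | 0.081 | 2.6% | 1.6% | 1.1% |

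For example, at 1 SD: 0.1455/1.6455 = 8.8%. A simulation of 4 million participants gave 20.5%, 8.8-8.9% and 2.6% for v = 0.

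**4. Spacing of tests.** Let Screen and BSL correlate at q, and pre-training tests with Post at r. The change-score reduction with no gate is 1 − [1 + (1 + q)/2 − 2r]/[2(1 − r)]. For q = 0.85 and r = 0.80 this is 1 − 0.325/0.40 = 18.7%. For q = 0.90 and r = 0.80 it is 1 − 0.35/0.40 = 12.5%. These correlations are assumed.

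**The case against.** The strongest objection is that the plan's own gate makes the two tests alike. When a participant is kept because Screen and BSL agree, their mean is close to BSL and averaging gains little. This stands. It means the 25% ceiling does not describe this trial if the gate excludes anyone. A reader might infer that the plan gives up a quarter of the variance, or the equivalent of a third more participants (1/0.75 = 1.33). The documents do not support either as an expected figure. On the other side, a cut-off tight enough to remove most of the gain would, on a single comparison, turn away a third or more of people whose true performance has not changed. The gain stays positive at every cut-off tried.

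Other limits also stand. BSL is the visit closest to training and, like the later visits, includes the full clinical and laboratory battery; Screen does not. Taking it as baseline is conventional, and nothing in the plan is contradictory or biased. Section 5.1 itself says that the Berg scale measures static balance and has a ceiling effect in higher-functioning people. It does not say whether the Screen walk is at self-selected or fastest pace, so a second value may exist for only one of the two.

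Two further inferences go too far. No passage says that Screen values are discarded; that is read from the list of periods. Nor do the documents show that initial walking speed rests on a single test, since its visit is unspecified. Error in that covariate would not bias a randomised comparison in any case.

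**Conclusion.** The point holds as an optional, low-cost improvement for two secondary outcomes, 10 m walking speed and the Berg score. The listed analysis leaves a usable pre-training test out of the baseline.

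The benefit lies between almost nothing and a ceiling of 25% of the variance of the arm difference in change. With assumed gates of 2, 1 and 0.5 SD it is about 20%, 9% and 3%. Varying individual responses or a stronger one-week correlation lower it further. All of these rest on assumed cut-offs, reliability and response spread, none of which the documents give.

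It should not be read as a weakness in the primary analyses. COM excursion and steps per day have no Screen value and gain no second baseline.

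**What to change.** Add one or two sentences to Section 5.6:

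- For the Berg score, and for the 10 m walk at whichever pace is recorded at Screen, take the mean of the two qualifying pre-training tests as baseline. Alternatively, enter both as repeated measurements of one pre-training visit in the mixed model.
- Where a third test was needed, use the two consecutive tests that met the stability rule. For this to be reproducible, the plan should state the rule's criterion.
- Use the same two-test mean as initial walking speed wherever that covariate appears. In the model for walking speed itself, enter the pre-training value once, either as outcome rows or as a covariate.

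No visit, test or participant burden is added. The one small downside is familiarisation. If people improve slightly from Screen to BSL simply by repeating the test, the pre-training mean shifts, but equally in expectation in both arms because training has not begun. The arm contrast is unaffected. Within-arm changes would be affected, so they should also be shown from BSL.
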